Additionally, all participants will receive a follow-up letter and report within 1 month of the visit that reiterate the evaluation results (i.e. BMI, blood pressure, urinary glucose, and spirometry) and recommended actions (Section 2.10.6, Follow-up Reports and

Information and Appendix P and Q). The participant's health care provider will also receive a copy of the report within one month of the encounter, if any significant abnormalities are detected and provided that the participant has indicated that they have a health care provider, consented to sharing this information with their provider, and have given their provider's name and contact information (Appendix O). For individuals in the Biomedical Surveillance Sub-cohort, CBC results and interpretations will be included in the report that accompanies the follow-up letter. Urgent findings identified by the laboratory will be phoned to individuals by the HVA or Call Center within one week of receipt from the laboratory (Section 2.10.6.3, Reporting of CBC Laboratory Tests).

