Alert levels for abnormalities associated with the CBC components that are reported to the participant (i.e., white blood cell count, hemoglobin concentration, hematocrit percentage or platelet count) will trigger “Urgent” referrals. Within one week of Alert Level findings being reported by the laboratory, participants will be notified by phone and advised to follow-up with a health care provider in either 72 hours for Alert Level 1 findings or one-to-two weeks for Alert Level 2 findings (as indicated in Table 2). The chosen laboratory urgent referral action levels were based upon values used for the Jackson Heart Study of African-American males and females ages 35-84 living in the Jackson, Mississippi area and reference values used by our central diagnostic laboratory. The Alert Level 1 referrals for total white blood cell count ($\leq 1.1 \times 10^3 / \mu\text{L}$), hemoglobin ($\leq 6.1 \text{ g/dL}$) and hematocrit ($\leq 18.1\%$) lead to a recommendation for participant follow-up in 72 hours. These thresholds are based upon the “panic levels” from our central diagnostic laboratory.

Spirometry Abnormalities:

Alert Level for post-exam spirometry interpretations will be reported to participants by phone within one week of receipt from the central laboratory. Participants will be advised to follow-up with a health care provider within one week (as indicated in Table 2). The spirometry alert level for an urgent referral utilizes the lower limits of normal (LLN) which is an index derived from population data based on race, age, sex, and height. The LLN is designed to be the 5th percentile for the index (FEV1, FVC, & Fev1/FVC) of interest (Roberts 2006). The use of FEV1 < 50% results in a “severe classification” regardless of obstructive or restrictive conditions and is consistent with ATS guidelines, assuming a valid and interpretable test (Pellegrino 2005). Given the nature of worker cohorts we do not expect to see very many participants in the severe category.

Table 2. Medical Care Referral Guidelines

Evaluation	Findings	Referral	Comments
Blood Pressure	SBP ≥ 180 or DBP ≥ 110	Urgent*. Seek care as soon as possible if confirmed as a chronic condition. *Based on AHA 2010 guidelines	HVA to offer to contact 911 or help assist with referral as indicated. HVA / Call Center to follow up with participant by phone ASAP.

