Spirometry	ALERT LEVEL Either FEV ₁ , FVC, or FEV ₁ /FVC below lower limits of normal AND FEV ₁ , < 50% predicted	Urgent Referral. See health care provider within one week. HVA / Call Center contacts participant by phone within	Participant advised to see HCP within one week of receiving phone call. Results mailed to participant within one month.

Evaluation	Findings	Referral	Comments
		one week of receiving spirometry evaluation	
	Either FEV ₁ , FVC, or FEV ₁ /FVC below lower limits of normal AND FEV ₁ , ≥ 50% predicted	Check-up. See health care provider within one month.	Results mailed to participant within one month.
	FEV ₁ , FVC, and FEV ₁ /FVC all above lower limits of normal	No Referral.	Results mailed to participant within one month.
CBC Total White Blood Cell Count	ALERT LEVEL 1* All: ≤ 1.1 x 10 ³	Urgent Referral. HVA / Call Center contacts participant by phone within one week of receiving results.	Participant advised to see HCP within 72 hours of receiving phone call for alert level 1. Letter with results mailed to participant within one month of receipt from lab.
	Results between alert level and normal reference range	Check-up. See health care provider within two months.	Letter with results mailed to participant within one month of receipt from lab.
	Within lab normal reference range	No Referral.	Letter with results mailed to participant within one month of receipt from lab.
CBC Hemoglobin	ALERT LEVEL 1* All: ≤ 6.1	Urgent Referral. HVA / Call Center contacts participant by phone within one week of receiving results.	Participant advised to see HCP within 72 hours of receiving phone call for alert level 1.
	ALERT LEVEL 2 Males: > 6.1 to 12 OR >20 Females: > 6.1 to 10 OR >17		Participant advised to see HCP within two weeks of receiving phone call for alert level 2. Letter with results mailed to participant within one month of receipt from lab.
	Results between alert level and normal reference range	Check-up. See health care provider within two months.	Letter with results mailed to participant within one month of receipt from lab.
	Within lab normal reference range	No Referral.	Letter with results mailed to participant within one month of receipt from lab.
CBC Hematocrit	ALERT LEVEL 1* All: ≤ 18.1	Urgent Referral. HVA / Call Center contacts participant by phone within one week of receiving results.	Participant advised to see HCP within 72 hours of receiving phone call for alert level 1.

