	ALERT LEVEL 2 Males > 18.1 to 35 OR >53		Participant advised to see HCP within two weeks of receiving phone call for alert level 2.

Evaluation	Findings	Referral	Comments
	Females > 18.1 to 30 OR >50		Letter with results mailed to participant within one month of receipt from lab.
	Results between alert level and normal reference range	Check-up. See health care provider within two months.	Letter with results mailed to participant within one month of receipt from lab.
	Within lab normal reference range	No Referral.	Letter with results mailed to participant within one month of receipt from lab.
CBC Platelets	ALERT LEVEL <50 x 10 ³ OR >500 x 10 ³	Urgent Referral. HVA / Call Center contacts participant by phone within one week of receiving results.	Participant advised to see HCP within two weeks of receiving phone call. Letter with results mailed to participant within one month of receipt from lab.
	Results between alert level and normal reference range	Check-up. See health care provider within two months.	Letter with results mailed to participant within one month of receipt from lab.
	Within lab normal reference range	No Referral.	Letter with results mailed to participant within one month of receipt from lab.

* Alert Level 1 for total white blood cell count, hemoglobin, and hematocrit are based on central diagnostic laboratory reference values.

Note: Other alert levels are based on a combination of central diagnostic laboratory reference values and alert values used for the Jackson Heart Study

If the participant has abnormal test results, the HVA will suggest appropriate follow-up with their healthcare provider. If the participant does not have a healthcare provider, they will receive referrals for medical and mental health care providers, as needed, including those providers that can assist with free or reduced-cost services (see Appendix N for example of Healthcare Provider Resource Information).

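### The CBC referral rules have no row for a high white cell count and give panic-level results the same one-week call limit as Level 2; Addendum 3 does not say whether they cover the LSU clinic CBCs

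*Protocol*

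**What the plan says.** Section 2.10.4.1 says that referrals and follow-up instructions are placed in one of five classes according to the participant's results, and points to Table 2 (Medical Care Referral Guidelines) for the limits.

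For the total white cell count, Table 2 has an Alert Level 1 row at or below 1.1 x 10^3, a check-up row for "Results between alert level and normal reference range", and a no-referral row for values within the reference range. The other CBC components have alerts on both sides. For men, the hemoglobin Level 2 row reads "Males: > 6.1 to 12 OR >20" and the hematocrit row "Males > 18.1 to 35 OR >53"; the upper limits for women are 17 and 50. Platelets alert below 50 or above 500 x 10^3.

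On timing, the CBC text of 2.10.4.1 sets one limit for both levels: "Within one week of Alert Level findings being reported by the laboratory, participants will be notified by phone". Sections 2.10.1 ("Urgent findings identified by the laboratory will be phoned to individuals by the HVA or Call Center within one week") and 2.10.6.3 repeat the one-week limit. The levels differ in the advice given at the call. Level 1 has "Participant advised to see HCP within 72 hours of receiving phone call for alert level 1"; Level 2 has "Participant advised to see HCP within two weeks of receiving phone call for alert level 2". The same section says the Level 1 limits for white cells, hemoglobin and hematocrit come from the diagnostic laboratory's panic levels.

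In Addendum 3, section 6.5.5 adds a CBC tube at LSU, and 6.12.1 sends it by courier within 24 hours to a testing laboratory. Section 6.13 and its Table 4 give actions for blood pressure, heart rate, BMI, spirometry, hemoglobin A1c and lipids. No CBC component appears there.

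**The concern.** A referral table works only if every possible value falls in a row. Here one direction of one component does not, and nothing in the text says the omission is deliberate. The protocol names hematologic effects among its outcomes of greatest interest (section 7.1), and section 2.10.4.1 says the investigators chose to be cautious because many participants lack access to care. A markedly raised white count is the one CBC extreme for which staff have no limit to act on.

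On timing, a panic level marks a result that should not wait. The protocol separates the two alert levels only after the participant has been reached. Before that, the stated limit is the same for both, so the more urgent level has no protected faster route to first contact.

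Addendum 3 matters because its section 4 describes the baseline CBCs as already done. The CBCs to which a corrected rule could still apply are those at LSU, and Addendum 3 does not say which CBC rule governs them.

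**Working it through.** The plan states no figure to reproduce. The check is a reading of row coverage and a sum of time limits.

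**White cell coverage (Table 2)**

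- At or below 1.1 x 10^3: Alert Level 1.
- Above 1.1 x 10^3 and below the lower reference limit: check-up within two months. The middle row runs from the alert level to the reference range; since the only alert is low, it covers low values only.
- Within the reference range: no referral.
- Above the upper reference limit: no row.

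The laboratory's numeric reference range is not given, and this result does not depend on it.

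**Other provisions that could catch a high count**

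- The mailed participant report (2.10.1, 2.10.4.1, 2.10.6.3, 8.1.7) carries CBC results, an interpretation and a recommended action. It needs no provider and no consent to share. It sets no high white cell cutoff, and Table 2 supplies no category for it to use.
- The provider letter (2.10.4.1) needs a named provider and the participant's agreement, and may take a month.
- The call for findings the laboratory itself identifies as urgent (2.10.1, 2.10.6.3) names no high white cell limit and has the same one-week maximum.
- The call in 8.1.7 is for clinically significant abnormalities left out of the results letters. White cell count is one of the reported components (2.10.4.1), so this call does not clearly reach it. It also has no deadline.

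**Maximum time from laboratory report to advised care**

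Inputs: call window of 7 days for both levels (2.10.4.1, Table 2); advice of 72 hours = 3 days for Level 1 and two weeks = 14 days for Level 2 (Table 2), each counted from the call.

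- Level 1: 7 + 3 = 10 days.
- Level 2: 7 + 14 = 21 days.
- Difference in the call window: 7 - 7 = 0 days.
- Illustration with a one-day Level 1 call window (an assumed value): 1 + 3 = 4 days, which is 10 - 4 = 6 days fewer.

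**LSU clinic CBCs**

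CBC rows in Addendum 3 Table 4: 0. Sentences in Addendum 3 that apply the main protocol's CBC rules to these results: 0.

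**The case against.** The best argument for leaving the text alone has four parts.

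First, a high white count is not ignored, because every participant with a CBC receives a report with an interpretation and an action. This stands. A reader might infer from the missing row that such a participant hears nothing; the documents do not support that. The report and letter templates are in appendices not shown, so their wording for a high count is unknown. What is missing is a stated cutoff and category.

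Second, one week is a ceiling, and the levels are meant to differ in the advice given. It is true that earlier calls are allowed, and the documents do not say that panic values are held for a week. But no sentence requires a faster call for Level 1, and the 72 hours do not begin until the call is made.

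Third, a reader might set the CBC window against the most urgent blood pressure tier, where the instruction is "HVA / Call Center to follow up with participant by phone ASAP". That comparison does not hold. The blood pressure participant has already been told in person by the home visit agent, who offers to contact emergency services; the call is a later follow-up, not first notice.

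Fourth, on Addendum 3, the main CBC rules are written for the Biomedical Surveillance Sub-cohort, and section 6.14 of the addendum describes the clinic exam as that sub-cohort's visit. Table 4 supports a form handed over at the visit, where an off-site CBC could not appear. This largely stands, and it reduces the gap to a missing cross-reference. The gap is still real: Addendum 3 section 4 also brings in about 2,500 invitees who were not tagged for that sub-cohort at baseline, and the 8.1.7 call names the central diagnostic laboratory while the addendum says only a testing laboratory.

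**Conclusion.** The point holds in two stated rules and one missing link. Table 2 leaves white counts above the reference range without a category, and no other provision supplies a cutoff. Level 1 CBC results have the same call ceiling as Level 2, which permits up to 7 days to first contact and 10 days to advised care. Addendum 3 lacks a sentence tying the LSU CBCs to the main rules.

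The day counts are maxima that follow from the protocol's own limits; they are not expected delays. The documents give no number of participants with a high white count or a Level 1 result, and none is estimated here. A reader might also take the LSU share of the roughly 4,000 planned clinic exams as the number of CBCs still to come. The documents do not support that: Addendum 6 speaks of remaining participants eligible for exams at LSU, so exams were already under way, and the number left is not stated.

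This is a participant-safety correction with no effect on inference. It is worth making because it is cheap and changes written rules that staff would follow.

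**What to change.** 1. In the white cell block of Table 2, add a high-side urgent alert and a check-up row for values between the upper reference limit and that alert. The diagnostic laboratory and the medical investigators should set the cutoff.
2. Set a Level 1 call window shorter than Level 2, for example one day from the laboratory report. Make the change together in section 2.10.1, the CBC text of 2.10.4.1, the CBC rows of Table 2 and section 2.10.6.3, so that the four places agree. The medical investigators should choose the time.
3. In Addendum 3 section 6.13, add a sentence that these CBC rules, including the call windows, apply to the LSU clinic CBCs, which are analyzed off-site and fall outside Table 4.

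The cost is two table rows, one time limit changed in four places, one cross-reference and a matching call trigger. The downside is a few more or earlier phone calls.

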2.10.5 Abnormal Findings Form

The HVA will document all evaluation findings in the CAPI system while they are conducting the visit. This CAPI module that collects evaluation findings will contain workflow features that prompt the HVA on how to proceed when abnormal findings are obtained. The HVA will review the actions and check the appropriate items on the checklist for cues as to subsequent steps to be taken depending on the findings or situation (Appendix J, Baseline Questionnaire, Section N). Once this information has been uploaded to the central database, selected responses will trigger further actions for the HVA and Coordinating Center staff, such as follow-up phone calls, follow-up letters, and assistance with referrals.

2.10.6 Follow-up Reports & Information

2.10.6.1 Follow-up of Urgent/Emergency Situations During In-person Encounter

If the HVA contacts 911 for an emergency situation, the HVA or Study Center representatives may immediately follow-up, or as soon as possible with respect to the situation, with the participant or their spouse to express our concern, check on their current condition and determine future interest and ability to participate in the study.

2.10.6.2 Follow-up Letters to Summarize Evaluation Findings and Encourage Recommended Actions

Within one month of the home visit, we will mail the participant a follow-up letter with a summary of their evaluation results (see Appendix P and Q). This letter will also contain information reiterating their results and recommended actions.

2.10.6.3 Reporting of CBC Laboratory Tests

For individuals in the Biomedical Surveillance Sub-cohort, selected components of the CBC results and interpretations will be included in the report that accompanies the follow-up letter. Urgent findings identified by the laboratory will be phoned to individuals by the HVAs or Call Center within one week of receipt from the laboratory. HVAs or Call Center staff will also follow-up with participants within two weeks of sharing the results by phone to see if they need additional assistance scheduling an appointment with a health care provider. The date of all follow-up mailings will be recorded in the data system, any returned mailings will be noted, and those that cannot be reached by mail will be contacted by phone, if possible. Results of follow-up phone calls, including dates and times of calls, responses, advice, and referrals given to participants will also be entered into the data system.

2.10.6.4 Reporting of Spirometry Results to Participants

For participants that complete spirometry evaluations, interpretations of their results will be included in the report that accompanies the follow-up letter. Alert Findings identified during evaluation of their measurements will be phoned to individuals by the HVAs or Call Center within one week of receipt from trained pulmonary study reviewers. Urgent Referrals for participants to see their HCPs within one week will have HVAs or Call Center staff follow-up with participants within two weeks of sharing the results by phone to see if they need additional assistance scheduling an appointment with a health care

provider. The date of all follow-up mailings will be recorded in the data system, any returned mailings will be noted, and those that cannot be reached by mail will be contacted by phone, if possible. Results of follow-up phone calls, including dates and times of calls, responses, advice, and referrals given to participants will also be entered into the data system.

2.10.6.5 Results Reporting to Physicians

If any of the participants' evaluation findings are abnormal and the participant has a health care provider and consents to sharing evaluation findings, we will mail the health care provider a cover letter explaining the study and a copy of the summary of results and recommended actions that was sent to the participant. This report will be sent to the health care provider within one month of the home visit along with relevant contextual information such as normal value ranges (see Appendix O) so that the physician can provide the appropriate care to their patients.

2.11 Laboratory Biospecimen Processing and Storage

Once the biospecimens have arrived in the Central Processing Laboratory they will undergo additional processing to separate out the various components (serum, plasma, cell fractions) and aliquoting of samples into small volumes for cryostorage, before being transferred to the long-term storage facility.

2.11.1 Central Laboratory Processing

Active Follow-up Sub-cohort Sample Processing: The ACD tube will be cryopreserved with 10% DMSO and aliquotted into cryovials, which will be subjected to programmed cryopreservation and stored in LN2. The Trace Metal and PAXgene samples will be frozen in their original tubes at -20°C. The serum and plasma will be aliquotted into cryovials and stored in LN2. The RBCs/buffy coat (from the 10 mL and 6 mL EDTA tubes) will be aliquotted into cryovials and stored in LN2. The 2 mL EDTA tube will be aliquotted as whole blood into cryovials and stored at -80°C or LN2. The urine and saliva samples will be aliquotted and stored at -80°C or LN2. The blood clots will be aliquotted and stored at -80°C or LN2. The hair samples and dust wipes will be stored at -20°C. Toenail samples will be stored with desiccant, under controlled ambient temperature and humidity.

Biomedical Surveillance Sub-cohort Sample Processing: Samples from persons tagged as eligible for inclusion in this sub-cohort will be processed in the same manner as those of the rest of the Active Follow-up Sub-cohort except that, promptly upon receipt at the central processing laboratory, 1) A portion of the urine sample will be sent to a diagnostic testing laboratory to undergo a more comprehensive dipstick urinalysis, 2) The 2 mL EDTA tube will be analyzed by the diagnostic laboratory for CBC with WBC differential, and 3) The ACD-B tube will undergo discontinuous density gradient centrifugation in the CPL to isolate the lymphocytes, which will be mixed with 10% DMSO, aliquotted, and subjected to programmed freezing and storage in LN2.

The CPL will prepare the accumulated samples for transport in bulk for archive storage at the NIEHS Repository. All samples will be transferred to the NIEHS Repository for storage in liquid nitrogen or -20°C/-80°C mechanical freezers, as appropriate for each sample, within one week of receipt.

2.11.2 Study Sample Long-Term Storage at the NIEHS Repository

Environmental Pathology Laboratories (EPL) is the contractor that operates the NIEHS Repository. EPL is located in Keystone Park, in close proximity to the NIEHS campus in the Research Triangle Park in North Carolina.

The EPL Repository is a state of the art storage facility which integrates structural, mechanical, electrical, HVAC, liquid nitrogen (LN₂), and backup and monitoring systems to maintain ideal storage temperatures. These systems ensure specimen integrity and long-term preservation while supporting the safe and efficient storage of frozen specimens.

EPL's Repository houses a wide variety of biological and environmental samples and provides storage space for frozen, refrigerated, and room temperature specimens and associated data. The 17,000 square foot facility provides space for ultra-low temperature mechanical and liquid nitrogen freezers, data and specimen storage, and a processing laboratory. Nearly 10,500 square feet of space is dedicated to frozen storage, with a capacity of approximately 185 ultra-low temperature mechanical and liquid nitrogen freezers depending on the types of specimens to be stored. Additionally, the facility has three -20°C walk-in freezers totaling 675 square feet of space. Currently, EPL has over 3.5 million frozen specimens stored in archival storage.

EPL has over 25 years experience managing and operating archives and repository storage facilities for government and commercial clients. EPL provides qualified professional and technical personnel, materials, equipment and facilities for the receipt and long term, secure storage of samples, packaging of the samples for shipment, processing requests for samples and for aliquoting and labeling new samples, as well as distributing requested data and specimens.

Aliquots of a given type will be divided across liquid nitrogen and -20°C/-80°C mechanical freezers, as appropriate for each sample, to maximize integrity of the samples during long-term storage and to reduce risk of complete loss due to freezer failure.

